CALCIFYING TENDINOPATHY OF THE ROTATOR CUFF: BARBOTAGE VS SHOCK WAVES

BOTCH (5775)

19/6/24

PROYECT BOTCH

RESEARCH PROJECT – BOTCH (5775) - Version 3 (19/06/2024)

CALCIFYING TENDINOPATHY OF THE ROTATOR CUFF: BARBOTAGE Vs SHOCK WAVES

DEPARTMENT: PHYSICAL MEDICINE AND REHABILITATION

1. Starting assumptions

Calcifying tendinitis (CT) of the rotator cuff is one of the most common pathologies in the clinical practice of Med. Physical Medicine and Rehabilitation. It is based on the accumulation of calcium hydroxyapatite, causing inflammation, pain and functional impotence.

The use of ultrasound in consultation has favored the diagnosis, classification and treatment in some cases. Regarding their classification, they are classified in 3 grades according to Bianchi Martinoli's classification.

For their treatment, rest, anti-inflammatory drugs (NSAIDs) and kinesitherapy are the first-line treatments. But in resistant cases, other therapies such as extracorporeal shock waves (ESWT) and or ultrasound-guided barbotage (US-PICT).

Currently, the use of these last two therapies tends to have better results in ultrasound types II and III. However, the results obtained with each treatment have not been compared.

Given the current situation regarding waiting times, knowing in which cases one or the other therapy should be indicated is very useful in order to avoid overloading the system and to give the patient the best possible treatment in the shortest possible time.

Starting hypothesis: Patients with CT, in its different degrees, who have received US-PICT as treatment, obtain the same VAS differences at 1 month, 3 months and 6 months as patients who received ESWT as treatment in the population.

2. Background and previous results

Shoulder pain is a very frequent complaint among adults. A large number of these are due to TC with prevalences close to 8%, especially in women aged 30 - 60 years (1).

Of the risk factors that we can assume, many consider that "hormonal abnormalities and/or autoimmune diseases such as hypothyroidism, diabetes mellitus and rheumatoid arthritis" (2) play an important role in the development and chronicity of TC (3).

The natural course of CT pathogenesis is currently incomplete. As discussed in the starting hypothesis, calcium hydroxyapatite deposition is the pathophysiological basis of CT. This deposit, as opposed to the first theories that described its appearance due to tendon degeneration, is not currently supported (4).

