Regarding the use of US-PICT, there are multiple studies that support this practice. They recognize it as "an effective and safe treatment in CT, since it produces a significant clinical and radiological improvement"(7). A study carried out in the year 2022, which retrospectively sought to study the results of this technique, culminated demonstrating a significant improvement in pain in patients treated with this technique (11).

Few studies have been conducted to determine which type of therapy is most effective in each case, with very mixed conclusions. In the 2014 systemic review by Louwerens et al, it was shown that both the use of high-energy ESWT and US-PICT are effective treatments in chronic cases of TC for patients with symptomatology longer than 6 months, however it gave greater effectiveness to ESWT.(12) However, [name] et al, in 2014 published a randomized study which concluded that "ultrasound-guided needling treatment was more effective in restoring function and short-term pain relief." (13)

The aim and desire of this study goes a bit further and is outlined below.

3. Main and secondary objectives

1. Main objective:

- The main objective is to compare the mean differences in VAS at 1 month, 3 months and 6 months according to the treatment received, US-PICT or ESWT in patients with TC according to the evolutionary stage of the lesion based on the Bianchi Martinoli classification.

2. Secondary objectives:

- To know if there are variations in functionality with the Latinen test, joint balance (ROM), PGI and CGI.
- To protocolize an attitude towards this type of pathology.
- To favor the use of hospital resources.

4. Design of the study

Design: We propose to conduct a **prospective experimental longitudinal analytical block randomized clinical trial**.

Study population, variables and inclusion-exclusion criteria.

Inclusion criteria:

- Patients aged 30 - 60 years.
- Omoalgia lasting more than 3 months.

- Radiographic and ultrasound visualization in both planes of calcification.
- Sizes > 5 millimeters (mm).

Exclusion criteria:

- Patients not meeting inclusion criteria.
- Presence of another evident cause of pain (joint degeneration, capsulitis, rotator cuff tendon ruptures...).
- Patient who has previously received ESWT or US-PICT.
- Contraindication of therapies: infection, drug allergies, cancer....

Variables to take into account:

- Age: years
- Sex: male/female
- Type of therapy: ESWT/barbectomy

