- Endocrine/rheumatologic diseases: hypothyroidism, diabetes mellitus and rheumatoid arthritis.
- Number of calcifications
- Size of calcifications: mm
- Previous treatments: Yes/ No
- Location of calcification: Supraspinatus, subscapularis, and infraspinatus.
- ROM: Flexion, abduction, and external and internal rotation (°).

- **Visual analgesic scale (VAS):** initial, at 1, 3 and 6 months.

- **Latineen test: initial, at 1, 3 and 6 months of each test variable and final score.**

Correlation of VAS levels and Latineen test: (14)

VAS of 0 - 2.5 → IL = 6 VAS of 2.5-5 → IL=10 VAS of 5-7.5 → IL 13 VAS of 7.5-10 → IL =14

- **Patient Global Impression of Improvement Scale (PGI-I)**
- **Global improvement impression scale (CGI - GI)**

Sample size

Accepting an alpha of 0.05 and a beta of 0.2 in a bilateral contrast, 28 subjects in each arm are required to detect a difference equal to or greater than 3 units on the VAS scale. A standard deviation of 5 is assumed. A loss-to-follow-up rate of 20% has been estimated.

Work plan

The protocol carried out was as follows:

1st Phase : in this first phase, patients will be collected according to the criteria set out above for a period of **12 months**. During this time, the patients will be explained the two possible treatments to be received and after signing the appropriate informed consent, **they will be divided into groups according to treatment (ESWT vs US-PICT) stratifying according to the Bianchi Martinoli classification: (I/II or III)**. The decision for each

treatment will be made randomly, **dividing the patients in a 1:1 ratio** according to whether they come to the initial consultation and the previous patient has received one or the other treatment.

The variables indicated above and in the table of variables will be collected from these patients.

	ESWT	US-PICT
Type I	14n	14n
Type II/III	14n	14n

In relation to **ESWT**, these will be given using a **15 mm transmitter in continuous mode with pressure at 3 bar, frequency 12Hz and 3000 impacts**. The number of sessions will be between 4 - 8 according to the patient's clinical condition with a rest between sessions of 5 to 10 days.

US-PICT will be performed with 1 session in which the following actions will be performed:

- First, a **suprascapular nerve block** will be performed with corticosteroid and anesthetic (3 ml of bupivacaine) in an ultrasound-guided manner.

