- Then **the calcification will be infiltrated** with 5 ml of local lidocaine and preloaded physiological saline solution under ultrasound guidance.
- Finally, **repeated suctioning** with physiological saline will be performed to extract the calcium in an echoguided manner.

The inclusion of patients in the study will be carried out by [name]. The barbotomy technique will be performed jointly by [name], [name] and [name]. The ESWT technique will be performed by Fst. [name].

2nd Phase: Subsequently, 3 revisions will be carried out. One at 1 month, 3 months and another at 6 months after the end of therapy. In these, the variables will be taken again as indicated in the table of variables.

Initial consultation	1 month	3 month	6 month
Age Gender Type of therapy Diseases Number of calcifications Size Previous treatment Location ROM (measurement with goniometer) VAS _{in} Latineen Test	ROM (measurement with goniometer)	ROM (measurement with goniometer)	ROM (measurement with goniometer) VAS _{6m} Latineen Test PGI – I CGI - GI

Table of variables

3rd Phase: The information collected will be synthesized and entered into the SPSS program to obtain the results. For these the following actions will be carried out:

[figure not shown]
- For an independent data design:
 - 2 groups: Student's t-test or Mann-Whitney U-test.
 - More than 2 groups: Analysis of variance or Kruskal-Wallis "H" test.
- For a paired data design:
 - 2 groups: Student's t-test for paired data or Wilcoxon test.
 - More than two groups: Analysis of variance for repeated measures or Friedman's test.

A new variable VAS difference (VASDIF) will be created later, with the data obtained, according to the following formula in order to evaluate the variation with the initial VAS levels.

[figure not shown]
$$\text{VAS}_{\text{in}} - \text{VAS}_{\text{xm}} = \text{VASDIF}_{\text{xm}}$$

Main variables: VAS, Test de Latineen y variables, PGI y CGI.
 Variable agrupadora: ESWT Vs US-PICT

Type I calcifications

Type II/III calcifications

All contrasts will be bilateral and those where $P < 0.05$ will be considered significant. Data will be collected, processed and analyzed with SPSS v.21 statistical software.

Limitations of the study

In order to be able to carry out the following study, the following limitations can be found.

1. Poor adherence to the study by the patients causing losses.
2. Increased waiting times due to ESWT saturation.

Ethical aspects

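### The analysis text lists Latineen (with its items), PGI and CGI as main variables beside VAS, although the objectives rank them as secondary, so a secondary scale could be presented as a main result

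*Combined protocol and SAP*

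**What the plan says.** Four places bear on which outcome is the main one.

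- **Section 3, main objective.** Only VAS is named: "The main objective is to compare the mean differences in VAS at 1 month, 3 months and 6 months according to the treatment received".
- **Section 3, secondary objectives.** The other scales are placed here: "To know if there are variations in functionality with the Latinen test, joint balance (ROM), PGI and CGI".
- **Section 1, starting hypothesis, and section 4, Sample size.** Both use VAS alone. The hypothesis is that patients given US-PICT "obtain the same VAS differences at 1 month, 3 months and 6 months as patients who received ESWT". The sample size targets a difference of 3 VAS units.
- **Section 4, Work plan, 3rd Phase.** The analysis text reads "Main variables: VAS, Test de Latineen y variables, PGI y CGI". It is followed by the treatment as grouping variable and by the two lesion categories, type I and type II/III.

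The words after Latineen in that last line bring in its separate items. The variable list in section 4 records them: "Latineen test: initial, at 1, 3 and 6 months of each test variable and final score". On testing, the 3rd Phase says "All contrasts will be bilateral" and calls any result with P < 0.05 significant. The plan gives no order of testing, no adjustment for multiple tests and no statement that one of the listed variables takes precedence.

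**The concern.** Three of the four entries in the main-variables line (Latineen, PGI, CGI) are secondary in section 3. Only VAS is main in both places, and nothing in the plan reconciles the two lists.

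The trial is meant to guide which therapy to indicate in which patients, and one stated aim is a protocol for managing the condition. If VAS shows no difference but a Latineen item, PGI or CGI does, the 3rd Phase wording lets an author present that result as a main one. The objectives rank it lower, and the trial was not sized for it. The outcome that carries the recommendation could then be settled after the data are seen.

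**Working it through.** **Step 1: compare the two lists.**

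| Outcome | Section 3 | 3rd Phase line |
|---|---|---|
| VAS change | main | main |
| Latineen total | secondary | main |
| Latineen items | not named separately | main |
| PGI | secondary | main |
| CGI | secondary | main |
| ROM | secondary | not listed |

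The ranks conflict for Latineen, PGI and CGI. They do not conflict for ROM, which is nowhere called main.

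**Step 2: the plan's own figures.** The plan gives no error rate or number of tests, so there is no figure to reproduce on this point. The 28 per arm matters here only because it is built on VAS. Whether it follows from its stated inputs is a separate question.

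**Step 3: count the between-arm contrasts called main.** VAS is compared at 1, 3 and 6 months (section 3). Latineen is recorded at the same visits (section 4, variable list). PGI and CGI appear at 6 months in the table of variables. Each is taken once per lesion category (3rd Phase).

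- VAS only: 3 x 2 = 6.
- As the 3rd Phase line reads, total score only: (3 VAS + 3 Latineen + 1 PGI + 1 CGI) x 2 = 8 x 2 = 16.
- Latineen items would add more. They are left out, so 16 is a low count.

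**Step 4: chance of at least one false positive.** Assumptions: no true difference on any outcome; each test two-sided at 0.05; normal test statistics with a common correlation rho within a lesion type; independence between types, since they contain different patients. The documents give no correlations, so rho = 0.5 to 0.8 is an assumed range.

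For k contrasts within one type, with Z the shared normal component, Phi the normal distribution function and c = 1.96:

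p(k) = 1 - E{ [Phi((c - sqrt(rho) Z)/sqrt(1 - rho)) - Phi((-c - sqrt(rho) Z)/sqrt(1 - rho))]^k }

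Over both types: P = 1 - (1 - p(k))^2.

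| rho | p(3) | P, 6 VAS contrasts | p(8) | P, 16 contrasts | Increase |
|---|---|---|---|---|---|
| 0.5 | 0.125 | 0.235 | 0.250 | 0.438 | 0.203 |
| 0.7 | 0.109 | 0.207 | 0.191 | 0.345 | 0.139 |
| 0.8 | 0.098 | 0.187 | 0.158 | 0.290 | 0.103 |

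(P and the increase are computed from unrounded values.) For reference, with fully independent contrasts the two figures are 1 - 0.95^6 = 0.265 and 1 - 0.95^16 = 0.560.

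**Step 5: isolate the effect of the label.** The right comparison is 16 contrasts against the 6 that the main objective already implies: about 19-24% against 29-44%. The difference, about 10 to 20 percentage points, is what the longer list of main variables adds.

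**The case against.** The strongest reply is that the line may not rank outcomes at all. It stands directly above the grouping variable, in text about entering data in SPSS, and may simply list the dependent variables to be set against treatment. On that view the hierarchy is fixed in section 3, backed by a VAS-only hypothesis, a VAS-only sample size and VASDIF as the only derived outcome. This reading is possible and cannot be excluded. But the text does not say so, and section 3 has already used main and secondary as ranks, so a reader will naturally carry that meaning over. What is certain is an inconsistent label that leaves the ranking open.

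Three stronger readings are tempting, and the documents do not support them.

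- **That a significant Latineen item would settle the trial when VAS is null.** The plan has no rule for success. It says only when a contrast is called significant. Such a result could be presented as main; nothing says that it must be.
- **That the error rate rises from about 10% to 29-44%.** The 10% (1 - 0.95^2 = 0.0975) is for VAS at one visit in two lesion types. Using it as the baseline would charge the three VAS visits to this defect, although they come from the main objective itself.
- **That ROM's absence from the line is part of the contradiction.** ROM is secondary in section 3, so leaving it off a list of main variables agrees with the objectives.

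The plan also promises publication whatever the results. That limits non-publication, but it does not decide which outcome leads the report.

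**Conclusion.** The point stands as an inconsistency in the current text. The objectives, hypothesis and sample size make VAS the only main outcome, while the analysis text gives the same label to Latineen with its items, PGI and CGI, with no ranking. The consequence is a possibility that the wording leaves open: a secondary scale could be put forward as a main result.

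The cost in false-positive risk is about 10 to 20 percentage points (from 19-24% to 29-44%). It rests on assumed within-type correlations of 0.5 to 0.8, independence between lesion types and a count that omits the Latineen items. The inconsistency itself rests on none of these assumptions. It should be corrected before analysis.

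**What to change.** In section 4, Work plan, 3rd Phase, replace the main-variables line with: *Main variable: VASDIF. Secondary variables: Latineen total and items, ROM, PGI, CGI.* Add that the conclusion on which therapy is better rests on VASDIF only. Report the secondary variables as between-arm estimates with 95% confidence intervals, and do not describe them as main or confirmatory results.

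This removes the extra outcomes from the main family. It does not bring the error rate to 5% or 10%: VASDIF is defined for each visit, so six main contrasts (3 visits x 2 lesion types) remain, at about 19-24% under the same assumptions. Choosing among visits and lesion types is a separate matter.

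The cost is a few lines of text, with no new data or patients. The sponsor gives up the option of claiming success on a secondary scale.

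### VAS change is compared at three visits by lesion type, each contrast at P<0.05, with no primary visit, testing order or treatment-by-type test to support a by-type conclusion

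*Combined protocol and SAP*

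**What the plan says.** All places are in the combined protocol and SAP.

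- **Section 1, Starting assumptions.** The hypothesis is that patients with calcifying tendinopathy "in its different degrees, who have received US-PICT as treatment, obtain the same VAS differences at 1 month, 3 months and 6 months" as those given ESWT. The motive is "knowing in which cases one or the other therapy should be indicated".
- **Section 3, objectives.** "The main objective is to compare the mean differences in VAS at 1 month, 3 months and 6 months according to the treatment received", and this is done "according to the evolutionary stage of the lesion based on the Bianchi Martinoli classification". A secondary objective is "To protocolize an attitude towards this type of pathology".
- **Section 4, list of variables.** "Visual analgesic scale (VAS): initial, at 1, 3 and 6 months".
- **Section 4, Work plan, 1st Phase.** Patients are allocated 1:1, "stratifying according to the Bianchi Martinoli classification: (I/II or III"). The table there shows Type I and Type II/III, with 14 patients in each treatment-by-type cell. The two places group the types differently, but both give two strata.
- **Section 4, Work plan, 3rd Phase.** VASDIF is the baseline VAS minus the VAS at a given visit. Treatment is the grouping variable, and Type I and Type II/III are listed under it. The tests are a general menu: t-test or Mann-Whitney, ANOVA or Kruskal-Wallis, and paired versions including repeated-measures ANOVA. The decision rule is "All contrasts will be bilateral and those where $P < 0.05$ will be considered significant".

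The contrasts are not listed one by one, and two figures in the 3rd Phase text are not shown. The readable text gives no primary visit, testing order, adjustment or treatment-by-type test.

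**The concern.** Two gaps meet in the main objective.

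First, three visits are compared within each lesion type and none is named as decisive. Any one of them below 0.05 can be reported as the answer, so a chance finding has three openings per type.

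Second, the trial is meant to show which therapy suits which lesion, but the readable plan offers only separate comparisons within each type. Comparing the arms within a type is a legitimate estimate for that type. A significant result in one type and a non-significant one in the other is not evidence that the types differ. Read that way, it could be written into the treatment pathway the trial hopes to produce, even if the true effect is the same in both types. Likewise, a non-significant contrast could be taken as confirming the starting hypothesis of equal VAS change.

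**Working it through.** **Inputs from the documents.** Two-sided 0.05 per contrast (3rd Phase); three visits (section 3); two strata and 14 per cell (1st Phase); 3 VAS units, SD 5, power 80%, 20% loss, 28 per arm (Sample size).

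**Assumptions.** The between-visit correlation ρ of VASDIF is not given; 0.5 to 0.9 is assumed. If baseline and follow-up VAS have equal variances σ² and a common correlation c, two change scores have covariance σ²(1−c) and variance 2σ²(1−c), so ρ = 0.5. That points to the upper end of the error rates below.

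**1. The plan's own figure.** n per arm = 2 × (1.960 + 0.842)² × SD² / 3².
- SD 5: 43.6, so 44, or 44/0.8 = 55 after loss. The stated 28 is not reproduced.
- SD 4: 27.9, so 28 before loss.
- SD 3.5: 21.4, so 22, and 22/0.8 = 27.5, so 28 after loss.

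This mismatch is a separate matter. It is used here only to justify showing SD 5, 4 and 3.5.

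**2. False-positive rate with no true difference.** For three equally correlated two-sided z tests in one type:

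a = 1 − ∫ φ(u) [Φ((1.96 − √ρ·u)/√(1−ρ)) − Φ((−1.96 − √ρ·u)/√(1−ρ))]³ du.

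The two types are different patients, so over both the rate is 1 − (1 − a)².

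| ρ | one type, 3 visits | both types, 6 contrasts |
|---|---|---|
| 0 (ceiling) | 1 − 0.95³ = 14.3% | 1 − 0.95⁶ = 26.5% |
| 0.5 | 12.5% | 23.5% |
| 0.8 | 9.8% | 18.7% |
| 0.9 | 8.4% | 16.0% |

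If only 6 months is tested, over two types: 1 − 0.95² = 9.75%. Simulated t-tests with 14 per cell give nearly the same: 12.7% and 23.9% at ρ = 0.5, and 8.5% and 16.2% at ρ = 0.9.

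**3. Same 3-unit effect in both types, one visit.** Power p within a type comes from the noncentral t with 26 df and noncentrality 3/(SD·√(2/14)). The chance of significance in exactly one type is 2p(1−p). Interaction power, for a 3-unit difference between the types' effects, uses SE = SD·√(4/14) and 52 df.

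| SD | p | exactly one type | interaction power | 95% CI half-width within a type |
|---|---|---|---|---|
| 5 | 0.333 | 44% | 20% | 3.9 |
| 4 | 0.480 | 50% | 28% | 3.1 |
| 3.5 | 0.588 | 48% | 35% | 2.7 |

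With 11 per cell (14 × 0.8 = 11.2), exactly one type is significant 39%, 47% and 50% of the time, and interaction power is 16%, 23% and 28%.

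**The case against.** **No stated error rate is breached.** A reader might infer that the plan promises 5% for the whole main objective and fails to deliver it. It does not: it sets a threshold per contrast, and the sample-size text speaks of one bilateral contrast. Each contrast does hold 5%. The criticism that stands is that no overall rate or hierarchy is defined.

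**Six tests need not be one family.** It is tempting to lead with 16-24% and require a correction over all six. The lesion types are disjoint patients and can be treated as separate questions; whether they must share one alpha is a contested convention. The better-founded figure is the 8-13% within one type.

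**The 44-50% is not a multiplicity effect.** It comes from small cells. Testing at 0.025 per type hardly changes it: 36%, 46% and 50% at SD 5, 4 and 3.5. That split also raises the chance that neither type is significant, under a true 3-unit effect in both, from 44% to 59% at SD 5 and from 27% to 41% at SD 4. The figure therefore argues for an interaction test and intervals, not for a smaller alpha.

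**ANOVA is on the menu.** It could carry an overall test or an interaction, and the four-cell table would suit it. But it is listed only as a general option, without treatment, visit or type terms, so it does not fill the gap.

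**Some of the plan cannot be seen.** Two figures in the analysis section are missing. The table of variables, as extracted, shows VAS only at baseline and 6 months. A reader might infer that VAS is not measured at 1 and 3 months. The list of variables and the main objective say otherwise and the table may be broken, so this calls for confirmation and is not a finding.

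**Conclusion.** The point holds in a limited form. For VAS change, the readable plan fixes no primary visit or testing order, and states no treatment-by-type test behind the by-type conclusions it wants to draw.

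The false-positive chance is about 8-13% within one lesion type, 16-24% if both types are treated as one family, and 9.75% over the two types if only 6 months is tested. These figures assume no true difference anywhere and, for the first two ranges, correlations of 0.9 to 0.5 that the documents do not supply. As a separate matter of low power, a common 3-unit effect would look type-specific at a given visit about 44-50% of the time with 14 per cell (SD 5 to 3.5; SDs below 5 are assumptions). Separate by-type P values therefore cannot show in which cases each therapy should be preferred.

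Confidence is moderate, because the contrasts are inferred from the objective and part of the section is not visible.

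**What to change.** Before the data are analysed:

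1. **Visits.** Name one primary visit for VASDIF. Within each lesion type, test the other visits after it in a fixed order, each at 0.05. State whether the two types are separate questions or share alpha. A split to 0.025 per type is optional.
2. **By-type claims.** Base any statement that the better therapy depends on lesion type on a prespecified treatment × type interaction on VASDIF at the primary visit, with type-specific 95% CIs. Label it exploratory, because its power for a 3-unit difference between types is only about 20-35%.
3. **Intervals.** Report the 95% CI for every VAS contrast, and do not read a non-significant result as equal VAS change.
4. **Confirmation.** Ask the sponsor to confirm that VAS is taken at 1, 3 and 6 months, as the list of variables says.

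**Cost.** This needs SAP text and the sponsor's decisions on the visit order and on alpha across types. Data collection does not change if VAS is already taken at all three visits. Fewer visits can be called significant, and a later visit in the order can be claimed only if the earlier one is significant. Power at the primary visit is unchanged at 0.05. If the optional split is chosen, within-type power for 3 units at 14 per cell falls from 33% to 23% at SD 5, from 48% to 36% at SD 4, and from 59% to 47% at SD 3.5.
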